2.3 Benefit/Risk Assessment

2.3.1 Risk Assessment

Tezepelumab has been well-tolerated with no identified risks in the completed clinical studies to date. No serious allergic reactions or anaphylactic reactions causally related to tezepelumab were reported in the Phase 2 and Phase 3 studies. Although TSLP suppression could theoretically have unanticipated immune-related side effects impairing host defense against certain infections, there is no clear preclinical or clinical evidence supporting such a role, and no safety signals related to infections have been detected in the tezepelumab program.

Mild problems following inactivated influenza vaccine may include soreness, redness, or swelling where the injection was given, as well as headache (low grade), fever, muscle aches, nausea, and fatigue ([CDC Influenza 2021](#)). Very rarely, as with all vaccines, anaphylaxis may occur.

2.3.1.1 Important Identified Risks

To date there are no important identified risks in the tezepelumab clinical development program.

2.3.1.2 Important Potential Risks

The mechanism of action of tezepelumab suggests potential inhibitory effects on immune responses mediated by Th2 cells, leading to the possibility of diminution of the host's protective response to infection.

Severe infections

Severe infections are defined as infections that are SAEs, require treatment with systemic antiviral medications, intravenous antibiotics or medications for helminth parasitic infection, or require permanent discontinuation of study intervention.

To mitigate the potential risk of severe infections eligibility criteria will exclude vulnerable participants, and included participants will be monitored for infection with complete blood counts, including differential white cell count throughout the study; and through standard AE/SAE reporting. Participants using immunosuppressive medication within 3 months prior to screening; who have a history of a known immunosuppressive disorder; who have a history

of clinically significant infection prior to screening; and who have known active or suspected tuberculosis either treated or untreated, will be excluded.

Parasitic infestation/infections

Tezepelumab may decrease the protective response to helminth infection by blockade of TSLP.

To decrease the risk of parasitic infestation or infection, participants who have a history of clinically significant infection prior to screening and at screening, and participants with untreated systemic helminth parasitic infections or those at significant increased risk of systemic helminth parasitic infestations will all be excluded.

Serious hypersensitivity/allergic reactions (including immune complex disease)

As with any large molecule therapeutics, administration of tezepelumab may result in systematic and/or local reactions. Systemic reactions to large molecule therapeutics can be IgE or non-IgE-mediated and are generally characterized by signs and symptoms such as skin rash, urticaria, pruritus, local or diffuse erythema, angioedema, fever, chills, cough, dyspnea, wheezing, bronchospasm, nausea/vomiting, diaphoresis, chest pain, tachycardia or bradycardia, and/or hypotension, which can all be severe or life-threatening. Effects typically occur during or within several hours after study intervention, but may be delayed.

To mitigate the potential risk of serious hypersensitivity reactions, during and after administration of tezepelumab, specific requirements for observing participants for AEs/SAEs and for monitoring vital signs before, during, and after administration of tezepelumab are included in the CSP. In addition, medical equipment to treat acute anaphylactic reactions will be immediately available and site staff will be trained to recognize and treat anaphylaxis.

The administration of a mAb can result in the formation of ADA. The occurrence of ADA could result in immune complex disease (Type 3 hypersensitivity reactions) with manifestations such as serum sickness, nephritis, and vasculitis, or altered tezepelumab levels or activity.

To mitigate the potential risk of immune complex disease participants will be monitored for the presence of ADA and confirmed immune complex disease through routine monitoring of AEs/SAEs. Participants with a prior history of immune complex disease will be excluded.

More detailed information about the known and expected benefits and potential risks of tezepelumab may be found in the current Investigator's Brochure.

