5.2 Exclusion Criteria

5.2.1 Study Eligibility

Participants are excluded from the study if any of the following criteria apply:

Medical Conditions

- 1 Clinically important pulmonary disease other than asthma (eg, active lung infection, bronchiectasis, pulmonary fibrosis, cystic fibrosis, hypoventilation syndrome associated with obesity, alpha 1 anti-trypsin deficiency, and primary ciliary dyskinesia) or ever been diagnosed with pulmonary or systemic disease, other than asthma, that are associated with elevated peripheral eosinophil counts (eg, allergic bronchopulmonary aspergillosis/mycosis, eosinophilic granulomatosis with polyangiitis (EGPA), hypereosinophilic syndrome), or prior history of immune complex disease.
- 2 Any disorder, including, but not limited to, cardiovascular, gastrointestinal, hepatic, renal, neurological, musculoskeletal, infectious, endocrine, metabolic, hematological, psychiatric, or major physical impairment that is not stable in the opinion of the Investigator and could:
 - Affect the safety of the participant throughout the study.
 - Influence the findings of the studies or their interpretations.
 - Impede the participant's ability to complete the entire duration of study.
- 3 Life-threatening asthma defined as episodes requiring intubation associated with hypercapnia, respiratory arrest, hypoxic seizures, or asthma-related syncopal episodes.
- 4 History of cancer
 - Participants who have had basal cell carcinoma, localized squamous cell carcinoma of the skin, or in situ carcinoma of the cervix are eligible provided that the participant is in remission and have had their curative therapy completed at least 12 months prior to Visit 1.

- Participants who have had other malignancies are eligible provided that the participant is in remission and have had their curative therapy completed at least 5 years prior to Visit 1.
- 5 Allergy to eggs, if egg based influenza vaccine will be administered.
- 6 History of anaphylaxis to any biologic therapy.
- 7 History of Guillain-Barré syndrome.
- 8 Known or suspected active tuberculosis either treated or untreated.
- 9 A helminth parasitic infection diagnosed within 24 weeks prior to Visit 1 that has not been treated with, or has failed to respond to standard of care therapy.

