- 10 Current smokers or participants with smoking history \geq 10 pack-years and participants using vaping products, including electronic cigarettes. Former smokers with a smoking history of < 10 pack-years and users of vaping or e-cigarette products must have stopped for at least 6 months prior to Visit 1 to be eligible.
- 11 History of alcohol or drug abuse within 12 months prior to the date of informed consent.
- 12 Major surgery within 8 weeks prior to Visit 1 or planned surgical procedures during the conduct of the study.

Prior/Concomitant Therapy

- 13 If on allergen immunotherapy, participants must be on a stable maintenance dose and schedule for at least 30 days prior to Visit 1 with no anticipated change in therapy during the conduct of the study.
- 14 Use of immunosuppressive medication (including but not limited to methotrexate, troleandomycin, cyclosporine, azathioprine, tacrolimus, mycofenolate mofetil, intramuscular long-acting depot corticosteroid, or any experimental anti-inflammatory therapy) within 3 months prior to Visit 1.
- 15 Receipt of immunoglobulin or blood products within 30 days prior to Visit 1.
- 16 Receipt of live attenuated vaccines 30 days prior to the date of randomization.
- 17 Receipt of influenza vaccine for season 2021/22 prior to Visit 1.
- 18 COVID-19 vaccination within 6 days prior to randomization.

Prior/Concurrent Clinical Study Experience

- 19 Participants with a known history of allergy or reaction to the study intervention formulations or influenza vaccine.
- 20 Receipt of any marketed or investigational biologic within 16 weeks or 5 half-lives prior to Visit 1, whichever is longer.
- 21 Receipt of any non-biologic investigational medication within 30 days or 5 half-lives prior to randomization, whichever is longer.

- 22 Previously received tezepelumab.
- 23 Concurrent enrollment in another drug-related interventional clinical trial.

Diagnostic Assessments

- 24 Any clinically significant abnormal findings in physical examination, vital signs, baseline ECG, hematology, clinical chemistry, or urinalysis during screening period, which in the opinion of the investigator, may put the participant at risk because of his/her participation in the study, or may influence the results of the study, or the participant's ability to complete entire duration of the study.

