- 25 Positive hepatitis B surface antigen, or hepatitis C virus antibody serology, or a positive medical history for hepatitis B or C. Participants with a history of hepatitis B vaccination without history of hepatitis B are allowed to enroll.
- 26 A history of known immunodeficiency disorder including a positive HIV test at V1, or the participant is taking antiretroviral medications as determined by medical history and/or participant's verbal report.
- 27 Positive SARS-Cov2 test during the screening period.
- 28 ALT or AST level \geq 2 times the ULN confirmed during screening period.

Other Exclusions

- 29 For women only - currently pregnant (confirmed with positive pregnancy test), breastfeeding, or lactating women.
- 30 Involvement in the planning and/or conduct of the study (applies to both AstraZeneca staff and/or staff at the study site).
- 31 Employees of the study center or any other individuals involved with the conduct of the study or immediate family members of such individuals.
- 32 Judgment by the investigator that the participant should not participate in the study if the participant is unlikely to comply with study procedures, restrictions, and requirements.

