5.2.2 At Randomization

Participants are excluded from randomization if any of the following criteria apply:

- 1 Asthma exacerbation during the screening period that requires treatment with oral corticosteroids or a hospitalization/emergency room visit for the treatment of asthma.
- 2 Acute illness or evidence of significant active infection (eg COVID-19) or known influenza infection during the current influenza season.

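### Section 2.3.1.2 of the protocol says participants at raised risk of systemic helminth infestation are excluded, but no criterion in Section 5.2 carries this out

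*Protocol*

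**What the plan says.** Protocol Section 2.3.1.2 names parasitic infection as an important potential risk, because blocking TSLP may weaken the protective response to helminths. It then lists who is kept out to reduce that risk. One group is "participants who have a history of clinically significant infection prior to screening and at screening". A second is participants with untreated systemic helminth infection. For the third, it says that "those at significant increased risk of systemic helminth parasitic infestations will all be excluded".

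In Section 5.2 the single helminth criterion is exclusion 9 of 5.2.1, which begins: "A helminth parasitic infection diagnosed within 24 weeks prior to Visit 1 that has not been treated with, or has failed to respond". It ends by referring to standard-of-care therapy.

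Section 4.1 says that participants who meet the eligibility criteria are randomized at Visit 3. Section 5 forbids waivers. Section 6.3.2 bars randomization of anyone who fails the criteria. Section 5.4 ties the recorded screen-failure reason to the inclusion and exclusion criteria.

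**The concern.** The risk section describes an entry protection, and the eligibility section should deliver it. Sites screen against the numbered list. If a protection appears only in the risk narrative, a participant who lives in or travels to a setting with high helminth exposure, and who has no diagnosed infection, meets no exclusion and can be randomized. The protocol would then credit itself with a mitigation that its working criteria do not contain. The issue is participant safety and internal consistency. It does not touch the estimation of antibody responses.

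**Working it through.** No sample-size, power or error-rate figure is involved. The check compares the text of the two sections and counts criteria.

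**Step 1. Count the criteria.** Section 5.2.1 numbers 1 to 32 and Section 5.2.2 numbers 1 to 2, so 32 + 2 = 34. Criteria that address risk of, or exposure to, helminth infestation: 0 of 34. Many of the 34 concern unrelated matters, so the denominator shows only that the whole list was read. The inclusion criteria in 5.1 do not cover the point either.

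**Step 2. Test each criterion that might reach the risk group indirectly.**

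| Criterion | What triggers it | Does it reach risk without infection? |
|---|---|---|
| 5.2.1 no. 9 | A diagnosed helminth infection, untreated or unresponsive | No |
| 5.2.1 no. 1 | "ever been diagnosed with pulmonary or systemic disease, other than asthma, that are associated with elevated peripheral eosinophil counts" | No. It needs a diagnosis. It might arguably reach a past systemic helminth infection, although no. 9 implies that treated cases were meant to be eligible |
| 5.2.1 no. 2 | A disorder, infectious ones included, that is not stable | No. Being at risk is not a disorder |
| 5.2.1 no. 24 | "Any clinically significant abnormal findings in physical examination, vital signs, baseline ECG, hematology, clinical chemistry, or urinalysis during screening period" | No. It needs an abnormal finding |
| 5.2.1 no. 32 | The investigator judges that the person "should not participate in the study if the participant is unlikely to comply with study procedures" | No. This judgment clause is limited to compliance |
| 5.2.2 no. 2 | It opens: "Acute illness or evidence of significant active infection (eg COVID-19"; it also covers influenza this season | No. It needs a present illness or infection, or influenza this season |

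Visit 1 eosinophil counts are not redacted (Section 8.2.4, Table 9 footnote a). With no. 24, an eosinophilic infection could therefore be caught before dosing. That detects infection; it does not exclude people at risk of acquiring one.

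**Step 3. Ask whether 2.3.1.2 is normally carried into 5.2.** It states six distinct infection-related exclusions.

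| Stated in 2.3.1.2 | Found in 5.2 | Result |
|---|---|---|
| Recent immunosuppressive medication | 5.2.1 no. 14 | Match |
| Immunosuppressive disorder | 5.2.1 no. 26 | Match |
| Tuberculosis | 5.2.1 no. 8 | Match |
| Untreated systemic helminth infection | 5.2.1 no. 9 with 5.2.2 no. 2 | Substantially covered |
| History of clinically significant infection | 5.2.1 nos. 1, 2, 8, 9, 25, 26, 27; 5.2.2 no. 2 | Partly covered |
| Raised risk of helminth infestation | None | Absent |

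The tally is 3 + 1 + 1 + 1 = 6. Three carry over directly, so the narrative was evidently meant to be implemented through the criteria. Helminth risk is the only one with no counterpart at all.

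**Step 4. List what acts after entry.** The protocol has a specific stopping rule for a helminth infestation that leads to hospital admission, and a general one for adverse events that endanger the participant (7.1). Helminth infections and severe infections are adverse events of special interest (8.3.6). The SAP refers to a dedicated helminth case report form page (7.3, Appendix C). Dosing is deferred for intercurrent illness (6.2.1.3), extra safety samples may be drawn (8.2.4), and eosinophil counts may be ordered for safety (6.3.4). None of these screens for helminth risk before entry.

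**The case against.** The strongest reply is that Section 2.3.1.2 is itself protocol text. Appendix C requires conduct in accordance with the protocol, and nothing in Sections 5 or 6.3.2 stops an investigator from declining a candidate thought to be at helminth risk. Those sections bar ineligible people; they do not compel entry. This stands against the stronger reading that a reader might infer, namely that the exclusion is void. The documents show two statements that do not agree, and an attentive investigator could act on the narrative one. It does not remove the point, because Section 4.1 randomizes those who meet the eligibility criteria and a site has no numbered criterion to cite.

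A second reply is that the safeguards after entry are substantial and partly helminth-specific, and that the protocol reports no infection signal in the program (2.3.1). Both are correct. They limit the consequence, but they are a different kind of protection from exclusion at entry.

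A third is that rewording 2.3.1.2 would also end the inconsistency. It would, but by withdrawing a measure that the sponsor chose to state. Adding the criterion implements it.

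A reader might also take the infection-history phrase as a second missing criterion. That goes too far. The phrase has no time limit or definition, and much of it is covered, for instance by "a positive medical history for hepatitis B or C" in exclusion 25. A resolved serious infection of an unnamed kind would not exclude, but this calls for editorial alignment and is not part of the main claim. Nor do the documents support saying that untreated helminth infection is uncovered.

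**Conclusion.** The point holds in limited form: an entry mitigation stated in 2.3.1.2 for participants at raised helminth risk is not carried into the criteria that sites apply. The gap is complete on that one item (0 of 34 criteria) and concerns safety and consistency only.

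The number of participants affected cannot be derived from the documents. It is assumed to be very small because the trial runs only in the USA, with about 100 randomized and four planned doses, plus one or two more if vaccination is delayed. The primary analysis is unaffected. A reader might infer that the overall benefit-risk conclusion in Section 2.3.3 fails without this measure. The documents do not support that: the section refers to the mitigation measures in general and does not turn on this clause.

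The change is worth making because it is cheap and gives effect to the sponsor's own stated intention.

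**What to change.** Add one exclusion to Section 5.2.1: participants who, in the investigator's judgment, are at significantly increased risk of systemic helminth infestation. As a separate editorial matter, align the infection-history phrase in 2.3.1.2 with the criteria that exist in 5.2.

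The cost is one criterion line and possibly a few more screen failures. The plan already allows for 135 − 100 = 35 screened participants who are not randomized, or 35/135 = 25.9%. The new line leaves the degree of risk to judgment, as 2.3.1.2 does now. The documents do not say whether enrollment was still open under this version. If it had closed, the criterion would protect no one further, and 2.3.1.2 should instead be corrected to describe the exclusions actually applied.

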2.3.2 Benefit Assessment

Benefits for tezepelumab over placebo include a clinically meaningful reduction in asthma exacerbations, improvement in lung function and asthma control metrics ([Corren et al 2017](#)).

Participants in this study may benefit from the continuous monitoring of all AEs arising during the clinical study, related or not related to the study intervention. In addition, participants will be contributing to the development of new therapies for moderate to severe asthma.

Benefits of seasonal influenza vaccination would include probable protection against developing influenza in the upcoming influenza season. GINA Guidelines recommend patients with moderate and severe asthma receive influenza vaccination every year to decrease risk of influenza and potential asthma exacerbation.

2.3.3 Overall Benefit: Risk Conclusion

Taking into account the measures taken to minimize risk to participants enrolling in this study (see [Section 2.3.1.2](#)), the potential risks identified in association with tezepelumab are justified by the anticipated benefits that may be afforded to participants with moderate to severe asthma.

3 OBJECTIVES AND ENDPOINTS

Please note: If influenza vaccine administration is delayed, some participants' assessments at Visit 6 (Week 12) and Visit 7 (Week 16) may be performed at later timepoints.

Table 3 Objectives and Endpoints

Objectives	Endpoints
Primary	

To evaluate the effect of tezepelumab on the humoral immune response following seasonal influenza virus vaccination in adolescent and young adult participants with moderate to severe asthma	
Post-dose strain-specific hemagglutination-inhibition (HAI) antibody geometric mean fold rises (GMFRs) from Week 12 (pre-dose antibody measure) to Week 16 (EOT)Post-dose strain-specific microneutralization (MN) antibody GMFRs from Week 12 (pre-dose antibody measure) to Week 16 (EOT)Post-dose strain-specific serum HAI antibody geometric mean titers (GMTs) obtained at Week 16 (EOT)Post-dose strain-specific serum MN antibody GMTs obtained at Week 16 (EOT)Post-dose strain-specific antibody response at Week 16 (EOT) with antibody response defined as a \geq 4-fold rise in HAI antibody titer from Week 12 (pre-dose antibody measure) to Week 16 (EOT)Post-dose strain-specific antibody response at Week 16 (EOT) with antibody response defined as a \geq 4-fold rise in MN antibody titer from Week 12 (pre-dose antibody measure) to Week 16 (EOT)Post-dose strain-specific HAI antibody titer \geq 40 at Week 16 (EOT)Post-dose strain-specific MN antibody titer \geq 40 at Week 16 (EOT)
Secondary	

To assess the PK and immunogenicity	
Serum trough tezepelumab concentrationsAnti-drug antibodies
Safety	

To assess the safety and tolerability of tezepelumab	
AEs and SAEsLaboratory variablesVital signs

Table 3 Objectives and Endpoints

Objectives	Endpoints
CCI	

Abbreviations: CCI

SAE=serious adverse events.

AEs=adverse events; PK=pharmacokinetic;

4 STUDY DESIGN

4.1 Overall Design

This is a Phase 3b, multicenter, randomized, double-blind, parallel group, placebo-controlled study designed to investigate the potential effect of tezepelumab (210 mg SC Q4W) on antibody responses following seasonal quadrivalent influenza virus vaccination in the fall/winter 2021-2022 in the USA.

Approximately 135 participants aged 12 to 21 years with moderate to severe asthma will be enrolled into screening to provide a target sample size of approximately 100 randomized participants for the study. Participants will be randomized 1:1 to receive tezepelumab 210 mg or placebo SC Q4W, administered at Weeks 0, 4, 8 and 12. Randomization will be monitored to ensure at least 50% of the enrolled participants are between the ages of 12 to 17 years.

Treatment allocation will be stratified by age at the time of informed consent/assent (12 to 17 years, and 18 to 21 years) to ensure equitable distribution of tezepelumab and placebo treatment in the 2 age groups. To ensure that at least 50% of the enrolled participants are 12 to 17 years old, the IWRS/IVRS will be set up with a 50% cap on the 18 to 21-year age group. Once this cap is reached, no more participants will be enrolled into the 18 to 21-year age group. Once an age group is closed, participants in the screening period in the closed age group will not be allowed to be randomized and will be considered a screen failure.

After enrollment and confirmation of entry criteria, participants will enter the screening period of a minimum of 2 weeks to allow adequate time for all of the eligibility criteria to be evaluated before being randomized. Participants who meet the eligibility criteria will be randomized at Visit 3 [Week 0] and will receive either tezepelumab 210 mg or placebo by SC injection at intervals of 4 weeks, ie doses of study intervention will be administered at Weeks 0, 4, 8 and 12. The study schema is presented in [Figure 1](#).

Participants will receive a single dose of inactivated quadrivalent seasonal influenza vaccine IM at Week 12, prior to the fourth dose of study intervention. Steady-state of tezepelumab is achieved at Week 12. Serum samples for evaluation of antibody response will be drawn at Week 12 (pre-vaccination) and at Week 16 (4 weeks post-vaccination) when humoral response to the vaccination is expected to be fully developed.

The EOT Visit will be conducted at Week 16 and a final Follow-up Visit and the End of Study Visit will be conducted at Week 28.

Please note: If influenza vaccine administration is delayed, the treatment period may be extended and therefore participants may be given an additional 1 to 2 study intervention doses (as needed) every 4 weeks for a longer period than initially planned.

Participants will be maintained on their currently prescribed ICS-LABA therapies without

change from enrollment throughout the screening and treatment period. If asthma exacerbations occur during the treatment period, participants can be treated with oral or other systemic corticosteroids or other asthma therapies according to standard practice.

4.1.1 Study Conduct Mitigation During Study Disruptions Due to Cases of Civil Crisis, Natural Disaster, or Public Health Crisis

The guidance given below supersedes instructions provided elsewhere in this CSP and should be implemented only during cases of civil crisis, natural disaster, or public health crisis (eg, during quarantines and resulting site closures, regional travel restrictions, and considerations if site personnel or study participants become infected with SARS-CoV-2 or similar pandemic infection) which would prevent the conduct of study-related activities at study sites, thereby compromising the study site staff or the participant's ability to conduct the study. The investigator or designee should contact the study sponsor to discuss whether the mitigation plans below should be implemented.

To ensure continuity of the clinical study during a civil crisis, natural disaster, or public health crisis, changes may be implemented to ensure the safety of study participants, maintain compliance with Good Clinical Practice, and minimize risks to study integrity.

Where allowable by local health authorities, ethics committees, healthcare provider guidelines (eg, hospital policies) or local government, these changes may include the following options:

- Obtaining consent/reconsent for the mitigation procedures (note, in the case of verbal consent/reconsent, the ICF should be signed at the participant's next contact with the study site).
- Re-screening: One additional re-screening to confirm eligibility to participate in the clinical study can be performed in previously screened participants. The investigator should confirm this with the designated Parexel Medical Monitor.
- Home or Remote visit: Performed by a site qualified HCP or HCP provided by a TPV only during safety follow-up (after Visit 7).
- Telemedicine visit: Remote contact with the participants using telecommunications technology including phone calls and virtual or video visits only during safety follow-up (after Visit 7).

For further details on study conduct during civil crisis, natural disaster, or public health crisis, refer to [Appendix B](#).

